# 7.1.4 Post-treatment Follow-up

All subjects will be followed for response until 1 year after the end of the M3541 / RT treatment period or earlier due to any reason whereby tumor assessments are no longer applicable (eg, if a new treatment is started, withdrawal of consent). All subjects will be followed for survival and for AEs (short term) and delayed AEs (late appearing RT-related toxicity) for up to 1 year after the end of the M3541 / RT treatment period, after which only delayed RT-related toxicity events will be collected. The post-treatment follow-up period is divided into:

- Short-term (PTD 22; ± 2 days and PTD 30; ± 2 days)
- Mid-term (PTDs 42 and 90; ± 7 days)
- Long-term (PTDs 126 and 180; ± 14 days)
- Survival follow-up / End-of-Study (PTDs 270 and 365; ± 21 days) visits
- Post 1-year Safety Follow-up to collect RT-related toxicity events every 3 months (± 1 month, telephone contact is acceptable) until the defined end of the study (see Section 5.7).

Subjects will be asked to return to the clinic on the designated days ( $\pm$  the visit window) for assessments as outlined in Table 1.

At any point during the post-treatment follow-up, if the subject withdraws from the study prematurely, the assessments scheduled for the Short-term Safety Follow-up (PTD 30) and End-of-Study visits should be performed.

#### 7.2 Demographic and Other Baseline Characteristics

The assessments and procedures described in this section must be performed during the Screening period.

# 7.2.1 Demographic Data

The following demographic data will be recorded:

- Date of birth
- Sex
- Ethnicity
- Race.

# 7.2.2 Diagnosis of Tumor

The tumor disease information that will be documented and verified at the Screening visit for each subject includes:

- Detailed history of the tumor, including histopathological diagnosis, grading and staging in accordance with the Union Internationale Contre le Cancer Tumor Node Metastasis Classification at diagnosis (UICC TNM)
  - $\circ~$  The M category (M0 or M1) of the tumor at the time of study entry, based on screening assessments
- All therapy used for prior treatment of the tumor (including surgery, radiotherapy and chemotherapy, immunotherapy, etc)
- Any other conditions that were treated with chemotherapy, radiation therapy, or immunotherapy
- Current cancer signs and symptoms and side effects from current and / or previous anticancer treatments
- Current cancer disease status.

# 7.2.3 Medical History

To determine the subject's eligibility to the study, a complete medical history of each subject will be collected and documented during Screening, which will include, but may not be limited to, the following:

- Past and concomitant non-malignant diseases and treatments
- All medications taken and procedures carried out within 30 days prior to Screening.

For the study entry, all the subjects must fulfill all inclusion criteria described in Section 5.3.1, and none of the subjects should have any exclusion criterion from the list described in Section 5.3.2.

#### 7.2.4 Vital Signs and Physical Examination

Vital signs including body temperature, respiratory rate, pulse (after 5-minute rest), arterial blood pressure (after 5-minute rest), and body weight will be recorded at study entry prior to any (scheduled) blood draw. Height will be measured at Screening only.

Physical examinations will be performed.

The ECOG PS will be documented during the Screening phase.

Document No. CC Object No. CC

# 7.2.5 CT or MRI Scans and Bone Scans for Tumor Assessment at Baseline

A CT scan or MRI (if MRI is used, CT of chest is mandatory) of the chest, abdomen, and pelvis (at a minimum and other established assessments of tumor burden if CT / MRI imaging is not sufficient for the individual subject; other regions as specifically required for specific tumor indications) will be performed within 28 days prior to study treatment start in order to document the baseline status of the tumor disease using RECIST 1.1 target and non-target lesions. If the results of a CT scan or MRI performed within 4 weeks prior to first treatment are available, the Screening CT / MRI does not need to be performed.

A brain CT / MRI scan (either, contrast preferred) is required at Screening if not performed within the previous 6 weeks. Thereafter, brain CT / MRI scan should be performed if clinically indicated by development of new specific symptoms.

A bone scan should be done at Screening as clinically indicated.

#### 7.2.6 Cardiac Assessments

A 12-lead ECG will be recorded at Screening. The ECG will be recorded after the subject has been in a supine position breathing quietly for 5 minutes and prior to any associated PK blood sampling. The ECG should be obtained using a Holter recorder. The ECG results will be used to evaluate the heart rate, atrial-ventricular conduction, QR, QT, and QTc intervals, and possible arrhythmias. All ECG and ECG extract results must be reviewed at the site by the Investigator or a medically qualified designee for clinical management of the subject.

The Investigator will judge the overall ECG interpretation as normal or abnormal. If abnormal, it will be decided if the abnormality is clinically significant or not clinically significant and the abnormality will be recorded on the eCRF. Any clinically significant ECG abnormality (cardiac assessment) will be recorded as an AE or SAE as appropriate (see Section 7.4.1 and subsections).

In presence of a Grade  $\geq$  3 QTc prolongation (QTc  $\geq$  501 ms and / or an increase with at least 60 ms over baseline, on 2 separate consecutive ECGs that cannot be explained by the underlying medical condition or concomitant therapy) the treatment with M3541 should be interrupted and the subject evaluated by a cardiologist. The IMP M3541 will be re-introduced only after recovery of QTc to  $\leq$  480 ms (Grade 1) if recovery is within 3 days and the QTc prolongation was deemed unrelated to M3541. In case of incomplete recovery (QTc between 480 and 500 ms) and in the presence of demonstrated clinical benefit to the subject, described as CR, PR, or a minor response (minor response being a regression of at least 20%), M3541 may be re-introduced if the QTc prolongation was deemed unrelated to M3541 and upon agreement with the cardiologist and in consultation with the Sponsor, and with the agreed expectation that the clinical benefit of resuming M3541 treatment with RT is greater than the potential risk.

Document No. CC

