- m. Tumor imaging by CT, MRI, or bone scan at baseline to document extent of lesions according to RECIST 1.1. Baseline tumor evaluation can be up to 28 days old when treatment starts. A brain CT / MRI scan (either, contrast preferred) is required at Screening if not performed within the previous 6 weeks.
- n. Tumor assessments using the same method used at baseline are to be completed every 6 weeks beginning on PTD 42 of the Mid-term Safety Follow-up period through the Long-term Safety Follow-up period (ie, PTD 180) for a total of 4 assessments. During the survival follow-up period (ie, PTD 181 to 365) tumor assessments will occur approximately on PTD 270 and PTD 365. Assessments are not required if the subject has started a new antitumor treatment. If a new treatment is started, the date (and regimen) must be reported in the eCRF.
- o. See Table 4 for details of PK blood sampling.
- p. FD 1 only; see Table 4 for details.
- q. FD 5 and 10; see Table 4 for details.
- r. CCI

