# 6.2.1 General Dose Modification and Discontinuation Guidelines

There is no intrasubject dose reduction or escalation planned for M3541. In general, each subject will stay on M3541 at the dose level and schedule assigned at study entry unless treatment needs

Document No. CC

Object No. CC

to be interrupted or stopped. If the Investigator believes that a TEAE is due to RT, M3541 will also be stopped.

Maximum delays or M3541 administrations missed within the complete 10-FD treatment period are:

- For the once per FD schedule:
  - If RT and M3541 treatment must be interrupted for ≥ 4 FDs, subjects must be discontinued from M3541
- For the thrice weekly schedule:
  - If M3541 cannot be administered on the scheduled day / time, the M3541 dose will be skipped
  - If RT and M3541 treatment must be interrupted for ≥ 2 FDs, subjects must be discontinued from M3541
- For the twice weekly schedule:
  - If M3541 cannot be administered on the scheduled day / time, then M3541 administration should until 24 hours later, and if not possible, the dose will be skipped
  - If RT and M3541 treatment must be interrupted for ≥ 1 FDs, subjects must be discontinued from M3541

M3541 should not be administered if no radiotherapy is scheduled for that day. If the subject must be discontinued from M3541; RT can be resumed at the discretion of the Investigator.

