
 
Systemic Toxicities, Other
 
Nonhematologic Toxicities 
 
Any Grade ≥ 3 toxicity, excluding:
 
Diarrhea (≤ 3 days duration) following adequate and optimal therapy
 
Nausea and vomiting (≤ 3 days duration) with adequate and optimal therapy
 
Fatigue or headache (< 7 days duration) following initiation of adequate supportive care
 
Any other single laboratory values out of the normal range that have no clinical significance, and that resolve to Grade ≤ 2 with adequate measures within 7 days
 
 
 
	Temporarily interrupt treatment. Resume treatment (at the same dose) once severity resolves to Grade ≤ 1 or baseline. See Section 6.2.1 for dose delay allowances.	Temporarily interrupt RT during M3541 interruption. If interruption is longer than allowed in Section 6.2.1, RT without M3541 can be resumed at the discretion of the Investigator.

AE = adverse event; ALT = alanine aminotransferase; AST = aspartate aminotransferase; CTCAE V4.03 = Common Terminology Criteria for Adverse Events, Version 4.03; FD = fraction day; IMP = investigational medicinal product; RT = radiotherapy; ULN = upper limit of normal

Note: Severity of AEs will be graded using the CTCAE V4.03 toxicity grades.

- a As all treatments with M3541 will be given in combination with RT, an interruption in the administration of RT would lead to an interruption in treatment with M3541.
- b A maximum RT interruption of ≤ 3 FDs in total is allowed within the complete treatment period. If RT / M3541 treatment have been interrupted by more than > 3 radiotherapy days, the subject must be discontinued from M3541. All effort should be made to complete 10 FDs if possible.

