Investigators must also systematically assess the causal relationship of AEs to IMP / study treatment (including radiation therapy) using the following definitions. Decisive factors for the assessment of causal relationship of an AE to the IMP / study treatment include, but may not be limited to, temporal relationship between the AE and the IMP / study treatment, known side effects of IMP / study treatment, medical history, concomitant medication, course of the underlying disease, study procedures.

- **Unrelated:** Not reasonably related to the IMP/study treatment. The AE could not medically (pharmacologically / clinically) be attributed to the IMP / study treatment under study in this clinical study protocol. A reasonable alternative explanation must be available.
- **Related:** Reasonably related to the IMP / study treatment. The AE could medically (pharmacologically / clinically) be attributed to the IMP / study treatment under study in this clinical study protocol.

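### Section 7.2.6 interrupts M3541 for a confirmed QTc rise of at least 60 ms but gives recovery only as QTc ≤ 480 ms, so at any baseline ≤ 420 ms the same QTc value can meet both

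*Protocol*

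**What the plan says.** Protocol Section 7.2.6 (Cardiac Assessments) works in three steps.

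- **Trigger.** Grade ≥ 3 QTc prolongation is QTc ≥ 501 ms and/or "an increase with at least 60 ms over baseline, on 2 separate consecutive ECGs", where disease or concomitant therapy does not account for it. M3541 is then interrupted and a cardiologist evaluates the subject.
- **Recovery.** M3541 "will be re-introduced only after recovery of QTc to" 480 ms or less, which the section labels Grade 1, "if recovery is within 3 days and the QTc prolongation was deemed unrelated to M3541".
- **Incomplete recovery.** A second path opens with "In case of incomplete recovery (QTc between 480 and 500 ms) and in the presence of demonstrated clinical benefit to the subject". Benefit means CR, PR or a regression of at least 20%. This path also requires that the prolongation be deemed unrelated to M3541, that the cardiologist agree, and that the Sponsor be consulted.

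Other relevant text:

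- Section 7.4.1.1 says of an unrelated event: "A reasonable alternative explanation must be available".
- For other systemic toxicities, Table 7 says "Resume treatment (at the same dose) once severity resolves to" Grade ≤ 1 or baseline.
- For the once per FD schedule, Section 6.2.1 says "If RT and M3541 treatment must be interrupted for ≥ 4 FDs, subjects must be discontinued from M3541".
- Exclusion criterion 7 in Section 5.3.2 sets no numeric limit on baseline QTc.
- SAP Section 9 defines baseline as the last non-missing value before the first M3541 dose.

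**The concern.** The trigger has an absolute limb and a rise limb, and the wording that joins them makes the rise limb sufficient alone. The recovery level answers only the absolute limb. A subject interrupted for the rise can therefore be at the written recovery level while the rise that caused the interruption is still present. The section then attaches two labels to one QTc value: Grade ≥ 3 by the trigger, and Grade 1 by the recovery level.

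The effect also runs the wrong way across subjects. The lower the baseline, the larger the rise that still counts as recovered.

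At stake is whether a subject is re-dosed while still meeting the protocol's own reason for stopping. This is a first-in-human study. Protocol Section 3.1.5 reports a half-life above 48 hours, against a predicted 8 hours, and accumulation in each subject, so earlier doses are still present when dosing resumes. In Table 4, scheduled ECGs on fraction days fall on FDs 1, 2, 5, 6, 7 and 10, so a restart on FD 3, 4, 8 or 9 has no scheduled ECG that day. SAP Section 15.7 tabulates QTcF increases above 60 ms separately from absolute QTcF, so the plan treats the rise as a signal in its own right.

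**Working it through.** The documents give no figure for this overlap, so there is none to reproduce. The check is threshold arithmetic.

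**Inputs** (Protocol Section 7.2.6): rise limb ≥ 60 ms over baseline; absolute limb ≥ 501 ms; recovery level ≤ 480 ms; incomplete-recovery band 480 to 500 ms. Let b be baseline QTc in ms.

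**Absolute limb.** A QTc ≥ 501 ms can never be ≤ 480 ms. It must fall by at least 501 − 480 = 21 ms, so this limb has no overlap.

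**Rise limb.**
- It is met when QTc ≥ b + 60.
- The recovery level is met when QTc ≤ 480.
- Both hold for QTc from b + 60 to 480, which needs b + 60 ≤ 480, so b ≤ 420.
- Largest rise compatible with the recovery level = 480 − b.
- Fall needed from the lowest triggering value = max(0, b + 60 − 480).

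| b (ms) | Lowest triggering QTc by rise | QTc meeting both | Largest rise at recovery level | Fall needed |
|---|---|---|---|---|
| 380 | 440 | 440–480 | 100 | 0 |
| 400 | 460 | 460–480 | 80 | 0 |
| 410 | 470 | 470–480 | 70 | 0 |
| 420 | 480 | 480 only | 60 | 0 |
| 421 | 481 | none | 59 | 1 |
| 440 | 500 | none | 40 | 20 |
| 450 | 510 | none | 30 | 30 |

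At baseline 440 ms, a subject who triggers at 500 ms must come down to a rise of 40 ms. At baseline 380 ms, a rise of 100 ms is within the recovery level.

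**480 to 500 ms path.** A rise of ≥ 60 ms inside this band needs b + 60 ≤ 500, so b ≤ 440. The rises possible in the band are 80–100 ms at b = 400, 50–70 ms at b = 430, 40–60 ms at b = 440, and at most 59 ms at b = 441.

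**Table 7.** It asks for Grade ≤ 1 or baseline. Because of the *or*, return to baseline is not required. Whether Grade ≤ 1 is met depends on which of the two labels in Section 7.2.6 is applied. Table 7 therefore passes the question back to that section.

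**The case against.** The strongest reply uses the grade labels. Section 7.2.6 itself calls a confirmed rise of at least 60 ms Grade ≥ 3. A subject who still has that rise is, on this definition, still Grade ≥ 3 and has not recovered to Grade 1. Table 7 can be read the same way, and the word *after* in "will be re-introduced only after recovery of QTc to" sets a sequence in which recovery follows interruption. On this view the wording is loose but the intent is clear.

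This is a fair reading, and it rules out two stronger claims that a reader might infer. One is that the ECG confirming the trigger automatically counts as recovery; the stated sequence makes that strained. The other is that Table 7 positively allows a residual rise; it does not say so. What remains is that the only number a site can apply is 480 ms, the section attaches Grade 1 to that number, and no sentence says that the rise must also clear.

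The other safeguards also have force. Section 7.2.6 excludes from the trigger prolongation that disease or other medication explains, yet restart requires the prolongation to be unrelated to M3541, and Section 7.4.1.1 demands an alternative explanation for that. Few causes fit both. Section 5.5.1 provides for withdrawal on safety grounds, and the SMC reviews ECGs. These limit how often the problem can arise. None sets a numeric limit on the residual rise.

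A reader might also infer that the 480 to 500 ms path can never be used, because tumor assessments "are to be completed every 6 weeks beginning on PTD 42 of the Mid-term Safety Follow-up period", after dosing has ended. That holds for scheduled assessments only: Section 7.3 also mentions clinically required imaging and caliper measurement of skin lesions.

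**Conclusion.** The inconsistency is real and minor. For every baseline of 420 ms or less, and for none above it, some QTc values satisfy both the rise trigger and the stated recovery level.

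The text does not support reading this as automatic re-dosing. Recovery is a necessary condition only, alongside the 3-day limit and the judgement that the prolongation is unrelated to M3541, and the cardiologist evaluates the subject as well. Nor do the documents support any claim about results: no analysis set, DLT estimate or model input is shown to change.

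The conclusion assumes that the joining words in the trigger mean that either limb suffices, as written, and that the SAP definition of baseline applies. The documents give neither a baseline QTc distribution nor an event rate, so the number of affected subjects cannot be estimated. The conditions for restart suggest that it is small. Exposure is bounded by the 10 FDs and, on the once per FD schedule, by the discontinuation rule in Section 6.2.1.

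**What to change.** In Section 7.2.6, define recovery as QTc ≤ 480 ms **and** a rise of less than 60 ms over baseline. In whole milliseconds the highest recovered value becomes min(480, b + 59): 439 at baseline 380, 459 at 400, 479 at 420, and 480 (unchanged) from 421 upward. No ECG can then meet both the trigger and the recovery level.

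Apply the same rise condition to the 480 to 500 ms path. For b ≤ 420 that path closes, since any value of 480 ms or more is then a rise of at least 60 ms. At b = 440 it stops at 499 ms (440 + 59). From b = 441 nothing changes, since 441 + 59 = 500.

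The added condition is modest. At baseline 400 ms, a subject who triggered at 460 ms would qualify at 459 ms. Its main effect is on the larger rises in the overlap; a wider margin would be a clinical decision.

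The change takes one clause in each of two sentences and no SAP amendment. The downside is that an occasional subject misses more M3541 doses, and one interrupted for 4 or more FDs on the once per FD schedule is discontinued from M3541 under Section 6.2.1.

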# 7.2.7 Clinical Laboratory Tests

Blood samples will be collected for clinical laboratory parameter evaluations. These clinical laboratory test results will serve not only as the baseline values for subsequent safety clinical laboratory evaluations during the study, but also help to make sure that each enrolled subject fulfills all the study entry criteria for laboratory parameters as listed in Section 5.3.1 and does not meet any of the study exclusion criteria as listed in Section 5.3.2. Detailed description of laboratory assessments is provided in Section 7.4.3.

# 7.3 Efficacy Assessments

For all subjects, tumor response assessment will be performed by CT scan or MRI (if MRI is used, CT of chest is mandatory) of the chest / abdomen / pelvis (plus other regions as specifically required for specific tumor types) and other established assessments of tumor burden if CT / MRI imaging is insufficient for the individual subject. All the scans performed at Baseline and other imaging performed as clinically required (other supportive imaging) need to be repeated at subsequent visits. In general, lesions detected at Baseline need to be followed using the same imaging methodology and preferably the same imaging equipment at subsequent tumor evaluation visits.

A brain CT / MRI scan (either, with contrast preferred) is required at Screening if not performed within the previous 6 weeks. Thereafter brain CT / MRI scan should be performed, if clinically indicated by development of new specific symptoms. A bone scan should be performed at Screening and beyond as clinically indicated. Skin metastasis can be used as target lesions according to RECIST 1.1 using measurements by caliper, if they fulfill RECIST 1.1 for target lesions as described below. The presence of new cutaneous lesions will be considered diagnostic of progression for RECIST 1.1, even if not imaged. For each subject, the Investigator will ensure appropriate assessment of the irradiated lesion to follow for determining response: CT or MRI images of primary and / or metastatic tumor masses, physical examination findings. All available images collected during the study period will be considered for the follow up of the subject (to determine further additional treatment needs). The measure(s) to be chosen for sequential evaluation during the study have to correspond to the measures used to document the progressive tumor status that qualifies the subject for enrollment. The tumor response assessment will be assessed and listed according to the Schedule of Assessments (see Table 1).

Bone scans are to be performed according to local and institutional standards.

The following endpoints will be derived based on appropriate tumor assessments according to RECIST 1.1 overall and for lesions within an irradiated field, including those after the end of study treatment until first assessment of PD:

• Progression-free survival: time from start of treatment to first assessment of PD or death, whichever is earlier. Subjects alive without PD will be censored at their last tumor assessment, documenting the overall objective response is either complete response (CR), partial response (PR), or stable disease (SD). This rule will also apply to subjects dying later than 12 or 26 weeks

Document No. CC Object No. CC

after their last tumor assessment (ie, censoring subjects who died after 2 missed tumor assessments)

- Objective Response: As assessed by the Investigator using RECIST 1.1
- SoLD: As assessed by the Investigator, using RECIST 1.1 on the irradiated target lesions
- Location of first relapse.

**Follow-up:** During survival follow-up (up to 1 year), further anticancer treatment as well as all subsequent progressions will also be recorded.

